1.4.2 Risk control in trial design

In the clinical study, a series of examinations (exams) at the screening and treatment period will be conducted. The frequency of the clinical laboratory (lab) tests such as blood biochemistry will be increased accordingly, if needed. Additional tests may be added, if deemed necessary. Additional risk to subjects include those attributable to study participation in general, including risks associated with frequent medical tests and laboratory blood draws, and the associated pain and discomfort.

Strategies to mitigate these risks include close monitoring of adverse events (AEs) and lab results. Both individual and trial stopping criteria will be specified, AEs will be assessed in this protocol, and AEs of special interest will be paid extra attention. Supportive care and risk control management will also be provided to subjects, including appropriate treatment of any AEs. The risk to participants in this trial will be minimized by adherence to the eligibility criteria, closely clinical monitoring and stopping rules.

Overall, the nonclinical data showed a positive benefit/risk ratio to support the clinical development of FWD1802 with appropriate safety monitoring. Data obtained from this

study will be provided to support later stages of clinical development for FWD1802 to be conducted in selected populations.

1.5 Clinical Study Compliance

This study will be conducted in compliance with this protocol, Good Clinical Practice (GCP), and all applicable regulatory requirements in United States

2 Objectives

Primary Objective:

- Establish the recommended phase II dose (RP2D) and/or the maximum tolerated dose (MTD) of FWD1802 as monotherapy and in combination with palbociclib in patients with ER+/HER2- unresectable locally advanced or metastatic breast cancer
- Explore the safety and tolerability of FWD1802 as monotherapy and in combination with Palbociclib

Secondary Objective:

- Characterise Pharmacokinetics of FWD1802 as monotherapy and in combination with palbociclib
- Explore preliminary efficacy signals

Exploratory Objective:

- Biomarker of FWD1802 as monotherapy and in combination with palbociclib

3 Endpoints

Safety should be evaluated at follow-up visits and throughout the study. Adverse events will be assessed for their severity (based on the NCI-CTCAE 5.0 rating), duration, and association with study treatment.

The following safety indicators will be measured and evaluated at designated intervals throughout the study. Patient history was taken at baseline to understand underlying conditions.

3.1 Safety and Tolerability

- Incidence of DLT in the MTD evaluation period, adverse events, treatment emergent adverse event (TEAE), serious adverse event (SAE), their relationship with the investigational product and respective severity.
- Changes in vital signs, ECOG score, ECG, physical examination, and laboratory tests before and after treatment, and the use of concomitant medication.

3.2 PK Assessment

- Maximum plasma concentration (C_{max}), Time to C_{max} (T_{max}), Area under the concentration versus time curve from time 0 to the last measurable concentration (AUC_{0-t}), The area under the plasma concentration-time curve from time 0 extrapolated to infinity (AUC_{0-inf}); if data permitted, elimination half-life time ($t_{1/2}$), apparent clearance (CL/F), apparent volume of distribution (V_z/F), and elimination rate constant (λ_z);
- Minimum concentration at steady state (C_{min_ss}), Maximum concentration at steady state (C_{max_ss}), Average concentration at steady state (C_{ave_ss}), $t_{1/2}$, CL/F , AUC_{tau_ss} , Volume at steady state (V_{ss}), elimination rate Constant (λ_z), accumulation ratio (AR) based on C_{max} and AUC_{tau_ss} ;

3.3 Efficacy Assessment

- Tumor response assessments by the corresponding criteria by RECIST v1.1 to assess Objective response rate (ORR), Clinical benefit rate (CBR), Duration of response (DoR), and Disease control rate (DCR) after the study treatment.

3.4 Exploratory endpoints

- The correlation between ER target inhibition by using [^{18}F]-fluorestradiol (FES) PET/CT and efficacy.
- Progression free survival (PFS) and Overall survival (OS).
- Other potential biomarker as needed.

4 Investigational Plan

4.1 Overall Study Design

This study is a multicenter, open-label, first-in-human study evaluating FWD1802 in patients with ER+/HER2- unresectable locally advanced or metastatic breast cancer. It includes three parts: the dose escalation of FWD1802 as a monotherapy study (Part A), the dose escalation of FWD1802 in combination with palbociclib study (Part B) and the dose expansion of FWD1802 as a monotherapy study in ESR1 mutation patients. (Part C). Part A: Dose Escalation: It aims to investigate the safety, tolerability, PK, PD, and preliminary efficacy in patients with ER+ /HER2- unresectable locally advanced or metastatic breast cancer who have failed or are intolerant of standard treatment, or have no standard therapy.

Part B: Dose Escalation: It aims to investigate the safety, tolerability, PK, PD, and preliminary efficacy in patients with ER+ /HER2- unresectable locally advanced or metastatic breast cancer who have failed or are intolerant of standard treatment, or have no standard therapy.

Part C: Dose Expansion: It aims to further evaluate the safety, tolerability, PK, PD, and preliminary efficacy of FWD1802 in approximately 60 eligible subjects with ER+ /HER2- unresectable locally advanced or metastatic breast cancer with ESR1 mutation under the dose level of the recommended dose for expansion(s) identified in part A study.

The overall study design is presented graphically in Figure 1. The detailed study procedures are provided in Section 7

[figure not shown]

Figure 1 Clinical Design of FWD1802 in Phase I Trial

4.2 Methodology

4.2.1 Part A – Dose Escalation of FWD1802 as a Monotherapy

Part A study will be conducted in subjects diagnosed with ER+/HER2- unresectable locally advanced or metastatic breast cancer, to evaluate the safety and tolerability, PK, PD and preliminary anti-tumor activity of FWD1802 Tablet, and to determine RDEs. A maximum of 27 subjects will be enrolled. They will be sequentially allocated to 5 planned dose cohorts: 25 mg, 75 mg, 150 mg, 300 mg and 450 mg.

Subjects enrolled will be orally administered a single dose of FWD1802 Tablet on Cycle 0 Day 1 (C0D1), followed by a 5-day observation period to evaluate the PK and safety of the drug product. Starting on Cycle 1 Day 1 (C1D1), FWD1802 Tablet will be orally administered continuously once or quaque die (QD) for 28 consecutive days of each cycle. The DLT observation period is set as 34 days after the initial administration (1 cycle) (single-dose period and the first 28-day cycle). The second cycle and subsequent cycles will last for 28 days per cycle. The patients will continue to receive the study treatment until disease progression, death, unacceptable toxicity, withdrawal of informed consent, or other reasons to discontinue study treatment occurs, whichever comes first.

Part A will utilize an accelerated dose escalation design to enroll one patient to dose levels 1, which will be converted to a traditional ‘3+3’ design when a grade 2 or higher toxicity occurs during cycle 1 therapy at these dose levels unless it is clearly related to disease progression or extraneous cause, whichever comes first.

Before starting the next dose level, all subjects (n=1, 3, or 6) at the current dose level must complete the DLT observation period. The Safety Monitoring Committee (SMC) will decide whether the study will proceed to the next dose level. Please refer to Section 4.7 Dose modifications.

Based on the safety data, a higher dose level beyond dose level 5 or an intermediate dose level can be explored as determined by the SMC.

The planned escalation dose levels are shown below:

Table 8. The Planned Dose Escalation Levels of FWD1802 in Phase Ia Study

Groups	Dose (mg) *	Percentage of escalation (%)	Number of subjects
1(Starting dose)	25	/	1~3
2**	75	200%	3~6
3**	150	100%	3~6
4**	300	100%	3~6
5**	450	50%	3~6

**Dose levels will be determined based on the results of lower doses, at the discretion of SMC.

4.2.2 Part B- Dose Escalation of FWD1802 in combination with palbociclib

The dose expansion study will be conducted in approximately 24 eligible subjects diagnosed with ER+/HER2- unresectable locally advanced or metastatic breast cancer, to

evaluate the safety, tolerability, PK, PD, and preliminary efficacy of FWD1802 in combination with palbociclib.

The starting dose level for Part B study will be determined by SMC based on safety data (including the AE rate of non-DLT), PK, PD and preliminary efficacy in Part A. Every treatment cycle consists of 28 days.

In brief, based on the available data obtained from Part A, 1 to 2 dose levels may be selected as the recommended dose levels (RDs) to evaluate FWD1802 in combination with palbociclib in these patients.

4.2.3 Part C – Dose Expansion Study

Part C (Dose Expansion of FWD1802 as a Monotherapy) can be conducted in parallel with Part A (Dose Escalation of FWD1802 as a Monotherapy) provided that the following two conditions are met:

- a) The starting dose of Part C study should be lower than the dose of monotherapy RP2D or the dose that has been explored and confirmed as safe for monotherapy.
- b) The SMC will review all available PK, PD, safety, tolerability and efficacy data for Part A study and decide whether the study may proceed to Part C portions.

The dose expansion study will be conducted in approximately 60 eligible subjects diagnosed with ER+/HER2-/ESR1 mutation unresectable locally advanced or metastatic breast cancer, to evaluate the safety, tolerability, PK, PD, and preliminary efficacy of FWD1802 Tablet at the recommended 1~2 dose level(s) for expansion.

The specific number of subjects, administration dose and dosing regimen in dose expansion study will be determined by SMC based on the results of Part A study.

4.3 Treatment Plan

Subjects will receive FWD1802 tablets orally according to the overall study design; the administration scheme is shown above. Subjects will continue to receive FWD1802 until any of the criteria specified in Section 5.4 Subjects Withdrawal Criteria are met.

Study drugs will be orally administered at the investigational site by site staff at 8 AM on the morning of the dosing days.

Note:the first group of FWD1802 in phase A study (25 mg) will be conducted on the preset conditions, while the dose levels, dosing schedule and biological sample collection time points for other groups might be modified upon emerging data in this study.

4.4 Dose Escalation/Stopping Criteria

The combination of ‘accelerated escalation’ and the traditional ‘3+3’ was used for Part A study. It’s planned that one eligible subject will be enrolled for the evaluation of the first

dose levels (25 mg) using intra-individual dose escalation, when it is approved by sponsor and investigator. If no \geq grade 2 adverse event (defined as any \geq grade 2 adverse event occurs during the DLT observation period unless it is clearly related to disease progression or extraneous cause) occurs during the DLT observation period, dose escalation enters the 2nd dose group with the traditional '3+3' mode. Otherwise, additional 2 subjects will be added to the current dose group, and the dose group and subsequent dose groups will switch to a '3+3' dose escalation design. Before starting the next dose level, all subjects (n=1, 3, or 6) at the current dose level must complete the DLT observation period and be determined by the Safety Monitoring Committee (SMC) to proceed to the next dose level. If no DLT has occurred at the end of the DLT observation period, subjects may adjust its dose level to any higher dose level that no DLT events have occurred during the DLT observation period, as assessed by the investigator and determined by the SMC, and on the condition that the investigator considers safe for the subjects.

If MTD cannot be determined at this part due to too few DLT events, a higher dose or an intermediate dose can be explored as needed, after the dose escalation reaches the highest predicted dose or is determined by the SMC.

The traditional '3+3' increment rule for dose escalation is as follows:

- The dose will be escalated if no DLT has been reported in the first 3 subjects of this dose group after DLT observation period.
- If 1 of the first 3 subjects enrolled has DLT occurred, then 3 additional subjects will be enrolled, with totally 6 subjects in this dose group.

-If only 1 DLT event occurs in these 6 subjects, then the dose will be escalated.

-If ≥ 2 DLT events occur in these 6 subjects, then no more subjects will be enrolled in this dose group and the dose escalation will be stopped. The SMC will decide whether to use the intermediate dose as the next dose level for the study or to terminate the dose escalation.

- If ≥ 2 DLT events occur in the first 3 subjects, then the dose escalation will be stopped, an intermediate dose or a lower dose level determined by the SMC will be selected as the next dose level for the study; or the dose escalation is terminated, according to the safety results of the enrolled subjects.

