4.5 Definition of MTD

- The maximum tolerable dose (MTD) is defined as the highest dose level while the incidence of DLT is less than 33% in the dose escalation study during the DLT evaluation period.
- Six patients are required to establish the MTD. If only 3 patients have been evaluated in the previous dose level below the non-tolerated dose, the cohort should be expanded to 6 patients at the previous dose level below the non-tolerated dose. If DLT is not observed in the additional 3 patients, or 6 patients have been evaluated at the previous

dose level, the MTD will be confirmed at the previous dose level below the non-tolerated dose.

- If MTD is not established at the end of escalation, the maximum safety dose will be defined as the maximum administrated dose (MAD).
- The recommended dose for expansion(s) will be confirmed comprehensively based on the results of safety, tolerability, PK and PD. The RP2D should be a pharmacologically active dose and the dose should be selected by pooling and evaluating all available PK, PD, target engagement, efficacy, safety, and tolerability data to select the appropriate dose. There will need to be at least 6 patients at the recommended dose for expansion level(s) to evaluate the safety, PK, PD and tolerability. If the DLT does not occur during the DLT assessment period, the current highest dose level will not be considered as the basis of dose escalation and may be used as a reference to dose design and safety evaluation of the recommend dose.

Based on the safety data, a higher dose level beyond dose level 9 or an intermediate dose level can be explored as determined by the SMC.

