4.6 Definitions of Dose-Limiting Toxicity (DLT)

All AEs of the specified grades should count as DLTs except those that are clearly and incontrovertibly due to disease progression or extraneous causes.

1. Hematological toxicity:

- CTCAE Grade ≥ 4 thrombocytopenia;
- CTCAE Grade 4 neutropenia lasting >7 days;
- CTCAE Grade ≥ 3 febrile neutropenia, where Grade 3 febrile neutropenia is defined as ANC $<1000/\text{mm}^3$ and a single temperature of $>38.3^\circ \text{C}$ (101°F) or a sustained temperature of $\geq 38^\circ \text{C}$ (100°F) for more than one hour;
- CTCAE Grade 3 thrombocytopenia ($\geq 25,000/\text{mm}^3$ and $<50,000/\text{mm}^3$) associated with bleeding;
- CTCAE Grade 4 ($<25,000/\text{m}^3$) thrombocytopenia lasting >5 days;

2. Non-hematological toxicity:

- Hy's law, defined as:
 - ✧ AST or ALT > 3 x the upper limit of normal (ULN) AND
 - ✧ Total bilirubin > 2 x ULN AND
 - ✧ Alkaline phosphatase < 2 x ULN AND

- ◇ No other reason for liver injury
- ALT or AST >8x ULN, ALT or AST >5x ULN for more than 2 weeks, ALT or AST >3x ULN and (TBL >2x ULN or INR >1.5)
 - ◇ For patients with hepatic metastases, AST or ALT > 8 x ULN or AST or ALT > 5 x ULN for \geq 14 days
- Grade > 3 non-hematologic toxicity with the exception of the following
 - ◇ Grade 3+ fatigue \geq 7 days regardless of baseline Grade;
 - ◇ Grade 3 nausea and vomiting, lasting \leq 2 days with optimal medical management;
 - ◇ Grade 3 diarrhea lasting \leq 3 days with optimal medical management
 - ◇ \geq 3+ non-hematologic abnormalities should also include laboratory values that cause symptoms.

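### The 3+3 rule in Protocol 4.4 counts subjects in one bullet and DLT events in three others, so one subject with two DLTs can trigger both expansion and stopping

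*Protocol*

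**What the plan says.** Protocol 4.4 gives the decision rule for each cohort after the accelerated first level:

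- No DLT in the first three: "The dose will be escalated if no DLT has been reported in the first 3 subjects of this dose group after DLT observation period".
- Expansion: "If 1 of the first 3 subjects enrolled has DLT occurred, then 3 additional subjects will be enrolled", giving six in all. The unit is the subject.
- After six, escalate: "If only 1 DLT event occurs in these 6 subjects, then the dose will be escalated". The unit is the event.
- After six, stop, on two or more: "DLT events occur in these 6 subjects, then no more subjects will be enrolled in this dose group and the dose escalation will be stopped". Here too the unit is the event.
- Within the first three, stop, on two or more: "DLT events occur in the first 3 subjects, then the dose escalation will be stopped". The unit is the event.

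Protocol 4.5 defines the MTD as "the highest dose level while the incidence of DLT is less than 33% in the dose escalation study". Protocol 4.6 opens with "All AEs of the specified grades should count as DLTs except those that are clearly and incontrovertibly due to disease progression or extraneous causes", so each qualifying adverse event is a DLT and one subject can have more than one. Nowhere does the protocol say that several DLTs in one subject count once, or that a DLT event means a subject with a DLT.

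**The concern.** A 3+3 rule should give exactly one action for each outcome. Here the expansion bullet and the first-three stopping bullet use different units, and both can be satisfied by the same data. The rule serves the primary objective (RP2D and/or MTD). According to the Synopsis, Part B also escalates by the 3+3 rule, and 4.4 is the only statement of it. Doses for Parts B and C are chosen from Part A. Section 5.5.1 also refers to the 4.4 stopping criteria as a ground on which the investigator may judge that the trial should end. If a committee followed the event wording, a level with one affected subject in six could be treated as not tolerated, and the MTD could be set too low.

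**Working it through.** **The plan's own figure.** One cohort of up to 3 and four of up to 6 give 3 + 4 × 6 = 27, the Part A maximum in 4.2.1. The cohort sizes are therefore as 4.4 describes.

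**Which bullets apply to the first three subjects.** Each triple gives the number of DLTs per subject.

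| Pattern | Subjects with a DLT | DLT events | Action under 4.4 |
|---|---|---|---|
| (0,0,0) | 0 | 0 | escalate |
| (1,0,0) | 1 | 1 | expand to 6 |
| (1,1,0) | 2 | 2 | stop |
| (2,0,0) | 1 | 2 | expand to 6 **and** stop |

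Only the last pattern (and any with more events in a single subject) conflicts. At zero the unit does not matter.

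**After six.** Suppose (2,0,0) is expanded and the next three have no DLT. Then 1/6 = 16.7% of subjects have a DLT, which is below 33%. The event count is 2, so the six-subject bullet stops escalation. With subjects as the unit, 4.4 and 4.5 agree: 1/6 = 16.7% is below 33% and 2/6 = 33.3% is not.

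**How often.** Two inputs are needed and the protocol gives neither, so both are assumptions: p, the DLT probability per subject, and q, the share of subjects with a DLT who have two or more.

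- Both first-three bullets apply: 3p(1−p)²q.
- Escalate, counting subjects: (1−p)³ + 3p(1−p)²(1−p)³.
- Escalate, counting events: (1−p)³ + 3p(1−p)²(1−q)(1−p)³.
- Difference: 3pq(1−p)⁵.

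At p = 0.10, 3p(1−p)⁵ = 0.3 × 0.59049 = 0.177. At p = 0.20 it is 0.6 × 0.32768 = 0.197. Multiplying by q gives the loss.

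| p | Escalate, subjects | Escalate, events (q = 0.1 to 0.3) | Loss, points | Both bullets apply |
|---|---|---|---|---|
| 0.10 | 0.906 | 0.888 to 0.853 | 1.8 to 5.3 | 2.4% to 7.3% |
| 0.20 | 0.709 | 0.689 to 0.650 | 2.0 to 5.9 | 3.8% to 11.5% |
| 0.30 | 0.494 | 0.479 to 0.449 | 1.5 to 4.5 | 4.4% to 13.2% |

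**Direction.** The number of events is never smaller than the number of subjects with an event. Event counting can therefore stop where subject counting would go on, but never the reverse.

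**The case against.** The best defence is that the intent is clear. The protocol calls the rule a traditional 3+3. The one bullet with an unmistakable unit counts subjects, and the two six-subject lines are sub-items of it. Incidence in 4.5 normally means a proportion of subjects. An experienced committee would probably count subjects, and the Safety Monitoring Committee (SMC) reviews every step. Most of this stands as evidence of intent. It does not remove the contradiction: three operative bullets say events, and the stop is worded as automatic. Once it applies, 4.4 leaves the SMC only an intermediate dose, a lower dose (in the first-three bullet) or termination. Nor can the matter safely wait for the SAP, which Section 10 requires only before database lock, possibly after the escalation decisions have been made.

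Three stronger readings are tempting, and the documents do not support them.

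- *Patients may be escalated past a toxic dose.* The direction of the error rules this out.
- *The overlapping liver criteria in 4.6 make the conflict easy to reach.* One hepatic episode may meet several lines, but 4.6 counts adverse events, not lines met. The protocol does not say that one episode is several DLTs. It does not exclude it either, so a clarifying sentence is worth adding.
- *The conflict will be common.* Nothing in the protocol supports a particular q. The only related figures, for fulvestrant plus palbociclib in 1.4.1, are 1% for Grade 4 thrombocytopenia and 0.9% for febrile neutropenia. They concern another drug over full treatment, so they are only indicative, but they lend no support to a large q.

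**Conclusion.** The contradiction is real and follows from the text alone, whatever p and q are. One subject with two separate DLTs among the first three is told both to expand and to stop, and a level with 1 of 6 subjects affected can halt escalation although it meets the 4.5 limit. The consequence is a possibly understated MTD or RP2D. A reader might infer that different MTDs must result; they do so only if the SMC applies the event wording literally. The size, about 2 to 6 percentage points of escalation probability per level, holds only for p of 0.10 to 0.20 and q of 0.1 to 0.3, both assumed. This is an internal inconsistency that should be fixed, not a flaw in the choice of design.

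**What to change.** Reconcile the 4.4 bullets with each other and with the incidence definition in 4.5, so that one counting unit is used throughout. Add one sentence saying how several DLTs in the same subject are counted, and how a single episode that meets more than one 4.6 criterion is counted. The traditional 3+3 label and the 4.5 definition both point to subjects with at least one DLT as the intended unit, but this is for the sponsor to confirm. State that the reconciled rule also governs Part B. The cost is a few wording edits in an amendment, with no added patients or procedures.

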4.5 Definition of MTD

- The maximum tolerable dose (MTD) is defined as the highest dose level while the incidence of DLT is less than 33% in the dose escalation study during the DLT evaluation period.
- Six patients are required to establish the MTD. If only 3 patients have been evaluated in the previous dose level below the non-tolerated dose, the cohort should be expanded to 6 patients at the previous dose level below the non-tolerated dose. If DLT is not observed in the additional 3 patients, or 6 patients have been evaluated at the previous

dose level, the MTD will be confirmed at the previous dose level below the non-tolerated dose.

- If MTD is not established at the end of escalation, the maximum safety dose will be defined as the maximum administrated dose (MAD).
- The recommended dose for expansion(s) will be confirmed comprehensively based on the results of safety, tolerability, PK and PD. The RP2D should be a pharmacologically active dose and the dose should be selected by pooling and evaluating all available PK, PD, target engagement, efficacy, safety, and tolerability data to select the appropriate dose. There will need to be at least 6 patients at the recommended dose for expansion level(s) to evaluate the safety, PK, PD and tolerability. If the DLT does not occur during the DLT assessment period, the current highest dose level will not be considered as the basis of dose escalation and may be used as a reference to dose design and safety evaluation of the recommend dose.

Based on the safety data, a higher dose level beyond dose level 9 or an intermediate dose level can be explored as determined by the SMC.

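### Section 4.5's MTD confirmation sentence does not match the section's own definition of the MTD, and it leaves a back-filled level with 1 DLT in 6 unclassified

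*Protocol*

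**What the plan says.** Establishing the RP2D and/or the MTD is a primary objective (Protocol, section 2). Section 4.5 defines the MTD as the "highest dose level while the incidence of DLT is less than 33% in the dose escalation study", counted over the DLT evaluation period, and adds: "Six patients are required to establish the MTD". If the level below a non-tolerated dose holds only three patients, it is expanded to six. The confirmation sentence follows: "If DLT is not observed in the additional 3 patients, or 6 patients have been evaluated at the previous" dose level, the MTD is confirmed at that level.

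Section 4.4 determines how a level comes to hold three or six patients. A level with 0/3 is passed with three. A level with 1/3 is expanded, passed at 1/6 and stopped at 2/6 or more. When escalation stops at six patients, "The SMC will decide whether to use the intermediate dose as the next dose level for the study or to terminate the dose escalation". When it stops within the first three, "an intermediate dose or a lower dose level determined by the SMC will be selected as the next dose level for the study" (or escalation ends). Section 4.5 also says that, if no MTD is established, the maximum safe dose is called the MAD. It closes by letting the SMC explore a higher or intermediate level on the safety data.

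**The concern.** A definition of below 33% in six patients has one cut-off: 0/6 or 1/6 qualifies, 2/6 does not. The confirmation sentence does not use it. For a level passed at 0/3 and back-filled later, it asks for no DLT among the three added patients, which amounts to 0/6. For a level that already holds six patients, it asks for nothing further, and such a level may stand at 1/6. The same 1/6 evidence is therefore confirmed if the DLT fell in the first three patients, and left without a stated outcome if it fell in the second three.

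This sentence is the operating rule for declaring the MTD. If the uncovered case arises, whoever declares the MTD must choose between the definition and the confirmation condition after seeing the data.

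**Working it through.** **Inputs from the Protocol.** Threshold below 33% and six patients (4.5); pass at 0/3, or at 1/6 after 1/3, and stop at 2/6 or more (4.4); confirmation sentence (4.5). The document gives no human DLT rates, so every rate p and every dose-toxicity curve below is an assumption.

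**Step 1: the definition at six patients.** 0/6 = 0%; 1/6 = 16.7%, below 33%; 2/6 = 33.3%, not below 33%; 3/6 = 50%. Section 4.4 agrees, since it escalates after 1/6 and stops at 2/6.

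**Step 2: every path by which escalation can have passed the level.** The natural reading takes the six-patient alternative to mean six before any back-fill. The literal reading includes the back-filled cohort.

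| First 3 + next 3 | Total | Meets definition | Natural reading | Literal reading |
|---|---|---|---|---|
| 0 + 0 | 0/6 | yes | confirmed | confirmed |
| 0 + 1 (back-fill) | 1/6 | yes | not covered | confirmed |
| 0 + 2 (back-fill) | 2/6 | no | not covered | confirmed |
| 0 + 3 (back-fill) | 3/6 | no | not covered | confirmed |
| 1 + 0 (in escalation) | 1/6 | yes | confirmed | confirmed |

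Neither reading reproduces the definition column. The natural reading misses 0 + 1; the literal reading lets in 0 + 2 and 0 + 3.

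**Step 3: the two orders of 1/6 are equally likely.** P(0/3 then 1/3) = (1−p)³ × 3p(1−p)² = 3p(1−p)⁵, and P(1/3 then 0/3) is the same product.

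| p | each order, 3p(1−p)⁵ | exactly 1 of the added 3, 3p(1−p)² | 2 or more of the added 3, 3p²(1−p)+p³ |
|---|---|---|---|
| 10% | 17.7% | 24.3% | 2.8% |
| 15% | 20.0% | 32.5% | 6.1% |
| 20% | 19.7% | 38.4% | 10.4% |
| 25% | 17.8% | 42.2% | 15.6% |

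The last two columns are conditional on a back-fill from 0/3.

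**Step 4: confirmation of a level that was passed and lies just below a non-tolerated dose.** P(passed) = (1−p)³ + 3p(1−p)⁵. On the natural reading, P(confirmed | passed) = [(1−p)⁶ + 3p(1−p)⁵] / P(passed). A rule of at most 1 in 6 adds a further 3p(1−p)⁵ to the numerator.
- p = 10%: (0.531 + 0.177)/0.906 = 0.782, rising to 0.977.
- p = 20%: (0.262 + 0.197)/0.709 = 0.647, rising to 0.925.

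**Step 5: whole trials.** Exact enumeration of the five-level 3+3 with three patients per cohort at every level. If a back-filled level has 2 or more DLTs, the next lower level is back-filled in turn.

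| Assumed true DLT rates, levels 1 to 5 | P(a back-fill ends at 1/6) |
|---|---|
| .01/.02/.03/.05/.08 | 1.0% |
| .02/.04/.06/.10/.15 | 4.8% |
| .02/.05/.10/.20/.35 | 17.3% |
| .05/.10/.20/.35/.50 | 24.7% |

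On the third curve, 16.65 points come from the first back-fill and 0.63 from step-downs. Section 4.2.1 says "Part A will utilize an accelerated dose escalation design to enroll one patient to dose levels 1". With one patient instead of three at 25 mg, the first-back-fill figure on that curve is 16.49%.

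**The case against.** A reader might infer that section 4.5 rejects a back-filled 1/6 level, so that the protocol makes the MTD depend on patient order. The text does not go that far. The sentence says if, not only if, and is silent on 0/3 then 1/3. The definition and the six-patient requirement, read alone, allow that level to be named the MTD, and section 4.4 treats 1/6 as tolerable. This part of the objection stands: the fault is a mismatch and a gap, not a prohibition.

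It can also be argued that the six-patient alternative has no word such as already, so a back-filled cohort satisfies it and order does not matter. That reading makes the zero-DLT condition redundant and puts no DLT limit on confirmation. Falling back on the definition to exclude 2/6 concedes that the confirmation sentence is wrong as it stands.

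A reader might further infer that the SMC has no route after a DLT in the back-fill. That is not so. The closing sentence of 4.5 lets it explore an intermediate level with no DLT-count trigger, and 4.4 gives it intermediate or lower levels once escalation stops. None of this text, nor the MAD provision, says how a back-filled 1/6 level is to be classified.

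Finally, the consequence is modest. The objective is the RP2D and/or the MTD, the RP2D is chosen on pooled data, and on the natural reading the error leans towards caution. All of that is right, and it limits the weight of the point.

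**Conclusion.** The confirmation sentence is wrong as written, because it conflicts with the section's own definition on either reading. The uncovered case is common once a back-fill from 0/3 occurs: 24% to 42% at assumed true rates of 10% to 25%. Over whole trials it ranges from about 1% to about 25% across the four assumed curves. The low end applies to a well-tolerated drug, a case that section 4.4 anticipates when it provides for too few DLTs to determine an MTD.

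The mismatch itself rests on no assumed rate; only its frequency does. The effect is limited to the MTD declaration. The documents do not support the inference that a wrong RP2D, or wrong Part B or Part C doses, would follow: the RP2D uses all available PK, PD, efficacy and safety data (4.5), and the SMC sets the later doses (4.2.2 and 4.2.3). The sentence should be corrected, but it does not threaten the design.

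**What to change.** Replace the confirmation sentence in section 4.5 with:

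*The MTD is confirmed at the previous dose level if no more than 1 of the 6 evaluated patients has a DLT, regardless of order; if 2 or more have a DLT, that level is non-tolerated and the same rule is applied at the next lower (or SMC-chosen intermediate) level.*

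This matches both the below-33% definition and section 4.4. The cost is one sentence, and no extra patients when the level is confirmed. After 2 or more DLTs in 6, the step-down may need 3 more patients at a lower level that holds 3. At 25 mg it may need up to 5 if only one patient was treated there, which exceeds that cohort's planned 1 to 3 (Table 8). The existing six-patient requirement already implies these patients. Per back-fill, the expected addition when the lower level holds 3 is 3 × 0.028 = 0.08 patients at an assumed rate of 10%, and 3 × 0.156 = 0.47 at 25%.
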